## **7. REPORTING OF ADVERSE EVENTS**

### **7.1 ASSESSMENT OF SAFETY**

Safety assessments will consist of monitoring and reporting adverse events (AEs) and serious adverse events (SAEs) that are considered related to study drug, all events of death, and any study specific issue of concern.

#### **7.1.1 Adverse Events**

An AE is any unfavorable and unintended sign, symptom, or disease temporally associated with the use of an investigational medicinal product (IMP) or other protocol-imposed intervention, regardless of attribution.

This includes the following:

- AEs not previously observed in the subject that emerge during the protocol-specified AE reporting period, including signs or symptoms associated with Basal Cell Carcinoma that were not present prior to the AE reporting period.
- Complications that occur as a result of protocol-mandated interventions (e.g., invasive procedures such as cardiac catheterizations).

If applicable, AEs that occur prior to assignment of study treatment associated with medication washout, no treatment run-in, or other protocol-mandated intervention.

Preexisting medical conditions (other than the condition being studied) judged by the investigator to have worsened in severity or frequency or changed in character during the protocol-specified AE reporting period.

### 7.1.2 **Serious Adverse Events**

An AE should be classified as an SAE if the following criteria are met:

- It results in death (i.e., the AE actually causes or leads to death).
- It is life threatening (i.e., the AE, in the view of the investigator, places the subject at immediate risk of death. It does not include an AE that, had it occurred in a more severe form, might have caused death.).
- It requires or prolongs inpatient hospitalization.
- It results in persistent or significant disability/incapacity (i.e., the AE results in substantial disruption of the subject's ability to conduct normal life functions).
- It results in a congenital anomaly/birth defect in a neonate/infant born to a mother exposed to the IMP.
- It is considered a significant medical event by the investigator based on medical judgment (e.g., may jeopardize the subject or may require medical/surgical intervention to prevent one of the outcomes listed above).

## 7.2 **METHODS AND TIMING FOR ASSESSING AND RECORDING SAFETY VARIABLES**

The investigator is responsible for ensuring that all AEs and SAEs that are observed or reported during the study are collected and reported to the FDA, appropriate IRB(s), and Genentech, Inc. in accordance with CFR 312.32 (IND Safety Reports).

### 7.2.1 **Adverse Event Reporting Period**

The study period during which all AEs and SAEs must be reported begins after informed consent is obtained and initiation of study treatment and ends 30 days following the last administration of study treatment or study discontinuation/termination, whichever is earlier. After this period, investigators should only report SAEs that are attributed to prior study treatment. Any subject who has an adverse event deemed related to the study treatment in this trial, will be followed until reversibility is established. This may occur after study completion at the subject's regular clinic follow-up visits.

### 7.2.2 **Assessment of Adverse Events**

All AEs and SAEs whether volunteered by the subject, discovered by study personnel during questioning, or detected through general skin examination, laboratory test, or other means will be reported appropriately. Each reported AE or SAE will be described by its duration (i.e., start and end dates), regulatory seriousness criteria if applicable, suspected relationship to the study drug (see following guidance), and actions taken.

To ensure consistency of AE and SAE causality assessments, investigators should apply the following general guideline:

#### **Yes**

There is a plausible temporal relationship between the onset of the AE and administration of study drug, and the AE cannot be readily explained by the subject's clinical state, intercurrent illness, or concomitant therapies; and/or the AE follows a known pattern of response to study drug; and/or the AE abates or resolves upon discontinuation of study drug or dose reduction and, if applicable, reappears upon re-challenge.

#### **No**

Evidence exists that the AE has an etiology other than the study drug (e.g., preexisting medical condition, underlying disease, intercurrent illness, or concomitant medication); and/or the AE has no plausible temporal relationship to study drug administration (e.g., cancer diagnosed 2 days after first dose of study drug).

Expected adverse events are those adverse events that are listed or characterized in the Package Insert or current Investigator Brochure.

Unexpected adverse events are those not listed in the Package Insert (P.I.) or current Investigator Brochure (I.B.) or not identified. This includes adverse events for which the specificity or severity is not consistent with the description in the P.I. or I.B. For example, under this definition, hepatic necrosis would be unexpected if the P.I. or I.B. only referred to elevated hepatic enzymes or hepatitis.

## 7.3 **PROCEDURES FOR ELICITING, RECORDING, AND REPORTING ADVERSE EVENTS**

### 7.3.1 **Eliciting Adverse Events**

A consistent methodology for eliciting AEs at all subject evaluation time points should be adopted. Examples of non-directive questions include:

- “How have you felt since your last clinical visit?”
- “Have you had any new or changed health problems since you were last here?”

### 7.3.2 **Specific Instructions for Recording Adverse Events**

Investigators should use correct medical terminology/concepts when reporting AEs or SAEs. Avoid colloquialisms and abbreviations.

#### 7.3.2.1 **Diagnosis vs. Signs and Symptoms**

If known at the time of reporting, a diagnosis should be reported rather than individual signs and symptoms (e.g., record only liver failure or hepatitis rather than jaundice, asterixis, and elevated transaminases). However, if a constellation of signs and/or symptoms cannot be medically characterized as a single diagnosis or syndrome at the time of reporting, it is ok to report the information that is currently available. If a diagnosis is subsequently established, it should be reported as follow-up information.

#### 7.3.2.2 **Deaths**

All deaths that occur during the protocol-specified AE reporting period regardless of attribution, will be reported to the appropriate parties. When recording a death, the event or condition that caused or contributed to the fatal outcome should be reported as the single medical concept. If the cause of death is unknown and cannot be ascertained at the time of reporting, report “Unexplained Death”.

#### 7.3.2.3 **Preexisting Medical Conditions**

A preexisting medical condition is one that is present at the start of the study. Such conditions should be reported as medical and surgical history. A preexisting medical condition should be re-assessed throughout the trial and reported as an AE or SAE only if the frequency, severity, or character of the condition worsens during the study. When reporting such events, it is important to convey the concept that the preexisting condition has changed by including applicable descriptors (e.g., “more frequent headaches”).

#### 7.3.2.4 **Hospitalizations for Medical or Surgical Procedures**

Any AE that results in hospitalization or prolonged hospitalization should be documented and reported as an SAE. If a subject is hospitalized to undergo a medical or surgical procedure as a result of an AE, the event responsible for the procedure, not the procedure itself, should be reported as the SAE. For example, if a subject is hospitalized to undergo coronary bypass surgery, record the heart condition that necessitated the bypass as the SAE.

Hospitalizations for the following reasons do not require reporting:

- Hospitalization or prolonged hospitalization for diagnostic or elective surgical procedures for preexisting conditions
- Hospitalization or prolonged hospitalization required to allow efficacy measurement for the study or
- Hospitalization or prolonged hospitalization for scheduled therapy of the target disease of the study.

#### 7.3.2.5 **Pregnancy**

If a female subject becomes pregnant while receiving investigational therapy or within 9 months after the last dose of VISMODEGIB, a report should be completed and expeditiously submitted to the Genentech, Inc. Follow-up to obtain the outcome of the pregnancy should also occur. Abortion, whether accidental, therapeutic, or spontaneous, should always be classified as serious, and expeditiously reported as an SAE. Similarly, any congenital anomaly/birth defect in a child born to a female subject exposed to the VISMODEGIB should be reported as an SAE.

#### 7.3.2.6 **Post-Study Adverse Events**

The investigator should expeditiously report any SAE occurring after a subject has completed or discontinued study participation if attributed to prior VISMODEGIB exposure. If the investigator should become aware of the development of cancer or a congenital anomaly in a subsequently conceived offspring of a female subject who participated in the study, this should be reported as an SAE.

#### 7.3.2.7 **Reconciliation of Study Drug Supply**

Investigators should conduct reconciliation for the product. Genentech and the investigator will agree to the reconciliation periodicity and format, but agree at minimum to exchange monthly line listings of cases received by the other party. If discrepancies are identified, the Sponsor and Genentech will cooperate in resolving the discrepancies. The responsible individuals for each party shall handle the matter on a case-by-case basis until satisfactory resolution.

#### 7.3.2.8 **SAE Reporting**

Investigators must report all SAEs to Genentech within the timelines described below. The completed Medwatch/case report should be faxed immediately upon completion to Genentech Drug Safety at:

**[contact]**

- Relevant follow-up information should be submitted to Genentech Drug Safety as soon as it becomes available.
- Serious AE reports that are related to study drug will be transmitted to Genentech within fifteen (15) calendar days of the Awareness Date.
- Serious AE reports that are unrelated to study drug will be transmitted to Genentech within thirty (30) calendar days of the Awareness Date.
- Additional Reporting Requirements to Genentech include the following:
- Any reports of pregnancy following the start of administration with VISMODEGIB will be transmitted to Genentech within thirty (30) calendar days of the Awareness Date.
- All Non-serious Adverse Events originating from the Study will be forwarded, at most, on a quarterly report to Genentech.

*Note: Investigators should also report events to their IRB as required.*

#### 7.3.3 **MedWatch 3500A Reporting Guidelines**

In addition to completing appropriate patient demographic and suspect medication information, the report should include the following information within the Event Description of the MedWatch 3500A form:

- Protocol description (and number, if assigned)
- Description of event, severity, treatment, and outcome if known
- Supportive laboratory results and diagnostics

- Investigator's assessment of the relationship of the adverse event to each investigational product and suspect medication

#### Follow-up Information:

Additional information may be added to a previously submitted report by any of the following methods:

- Adding to the original MedWatch 3500A report and submitting it as follow-up
- Adding supplemental summary information and submitting it as follow-up with the original MedWatch 3500A form
- Summarizing new information and faxing it with a cover letter including patient identifiers (i.e. D.O.B. initial, patient number), protocol description and number, if assigned, brief adverse event description, and notation that additional or follow-up information is being submitted (The patient identifiers are important so that the new information is added to the correct initial report)

Occasionally Genentech may contact the reporter for additional information, clarification, or current status of the patient for whom and adverse event was reported. For questions regarding SAE reporting, you may contact the Genentech Drug Safety representative noted above or the MSL assigned to the study. Relevant follow-up information should be submitted to Genentech Drug Safety as soon as it becomes available and/or upon request.

MedWatch 3500A (Mandatory Reporting) form is available at <http://www.fda.gov/Safety/MedWatch/HowToReport/DownloadForms/default.htm>

#### 7.3.4 **Additional Reporting Requirements for IND Holders**

For Investigator-Sponsored IND Studies, some additional reporting requirements for the FDA apply in accordance with the guidance set forth in 21 CFR § 600.80.

Events meeting the following criteria need to be submitted to the Food and Drug Administration (FDA) as expedited IND Safety Reports according to the following guidance and timelines:

##### 7 Calendar Day Telephone or Fax Report:

The Investigator is required to notify the FDA of any fatal or life-threatening adverse event that is unexpected and assessed by the investigator to be possibly related to the use of study drug. An unexpected adverse event is one that is not already described in the study drug Investigator Brochure. Such reports are to be telephoned or faxed to the FDA and Genentech within 7 calendar days of first learning of the event.

##### 15 Calendar Day Written Report:

The Investigator is also required to notify the FDA and all participating investigators, in a written IND Safety Report, of any serious, unexpected AE that is considered reasonably or possibly related to the use of study drug. An unexpected adverse event is one that is not already described in the study drug investigator brochure.

Written IND Safety reports should include an Analysis of Similar Events in accordance with regulation 21 CFR § 312.32. All safety reports previously filed by the investigator with the IND concerning similar events should be analyzed and the significance of the new report in light of the previous, similar reports commented on.

Written IND safety reports with Analysis of Similar Events are to be submitted to the FDA, Genentech, and all participating investigators within 15 calendar days of first learning of the event. The FDA prefers these reports on a Medwatch 3500 form, but alternative formats are acceptable (e.g., summary letter).

FDA fax number for IND Safety Reports:

Fax: [name]

All written IND Safety Reports submitted to the FDA by the Investigator must also be faxed to Genentech Drug Safety: [contact] or [contact]

And to the Site IRB:

**Saint Louis University  
Institutional Review Board**

[name]  
[name]  
[name]  
[contact]  
[contact]

For questions related to safety reporting, please contact Genentech Drug Safety:

[contact]

[contact] or [contact]

**IND Annual Reports**

All IND annual reports submitted to the FDA by the Sponsor-Investigator should be copied to Genentech. Copies of such reports should be faxed to Genentech Drug Safety: [contact] or [contact]

**7.4 Data Safety Monitoring Plan**

Due to the potential risk of adverse side effects, patients will be monitored closely during the study period as described in protocol Section 6, 7.1, 7.2 and section 12.7. Study participants will be able to contact one of the study physicians at any time with questions and concerns. All adverse events will be recorded, scored for severity and for relationship to the study as described in Section 7.3. Adverse event data will be reviewed periodically by the study team. All serious and unexpected adverse events will be reported to the IRB and regulatory authority as described in Section 7.3.

## 8. MATERIALS AND SUPPLIES

### 8.1 STUDY DRUG

Study drugs will be provided by Genentech or a designated facility working under contract for Genentech to Saint Louis University, Department of Dermatology.

Study drug should be taken at approximately the same time each day, with or without food. Capsules must be swallowed whole and must not be opened under any circumstances. If a patient misses a dose (e.g., due to emesis), he or she should be instructed not to take or make up that dose and to resume dosing with the next scheduled dose. Missed doses will not be made up. Patients will be instructed to bring all unused capsules to each study visit for assessment of compliance.

Sufficient drug supplies for 36 subjects will be packaged, and labeled. Drug supplies will be numbered in sequential order. The study center should assign study drug in sequential order. The remaining supplies will be made available should additional subjects or study centers be required to reach the enrollment goal of 36 total subjects.

Small, resealable plastic bags will be given to each subject for returning used and opened medication to the clinic. Resealable bags will be dispensed at the same time medication is dispensed.

At the Treatment Initiation Visit (Baseline/Day 1), and at the monthly interval, the study center will dispense a bottle of study drug to be used until the next interval visit at which drug will be dispensed.

At each time medication is dispensed:

- Dispense a resealable plastic bag
- Write the date dispensed on both sides of the 2-part label, located on the carton
- Affix the detachable portion of the 2-part label to the appropriate CRF page

All medication, both used and unused will be destroyed according to standard operating procedure at Saint Louis University at the completion of the study.

### 8.2 STUDY DRUG LABELING

Clinical supplies will be labeled with the following minimum information:

- Protocol ID Number
- Investigator Name
- Drug name (or description)
- Drug strength
- Dosage form
- Quantity per container
- Instructions for use
- Keep out of the reach of children
- Storage conditions

- Expiration date
- Investigational drug caution statement(s)
- Subject number
- Date dispensed (to be written in)
- Subject initials (to be written in)

Each time study drug is dispensed, study center personnel should write the date the drug is dispensed and the subject initials on both the permanent and detachable labels of the bottle. The study center should also complete the Drug Inventory Form each time study drug is dispensed.

### 8.3 **STUDY DRUG INVENTORY AND STORAGE**

The investigator will take the following actions with regard to study drugs in concurrence with international regulatory requirements.

1. Upon receipt of clinical study materials the investigator or designated individual on the study team will check the details of the supplies and document receipt on invoice and DAR.
2. The investigator will keep study drugs in a locked and secure storage facility, accessible only to those individuals authorized by the investigator to dispense this study drug. All study drug will be stored separately from any other medications.
3. The investigator or designee will maintain a temperature log to ensure that study drug is stored at manufacturer recommended room-temperature at all times.
4. The investigator or designated individual will maintain an inventory. This will include the description and quantity of study drug received during the course of this study, as well as a record of the materials that are dispensed and returned (how much, to whom, and when). This inventory record shall indicate the quantity and description of all study drugs on hand at any time during the course of the study.
5. At the conclusion or termination of this study, the investigator agrees to conduct a final drug supply inventory, to record the results of this inventory and destroy all remaining study drug on site by IDS.
6. The investigator agrees not to supply study drug to any person except study personnel and subjects in this study.

## 9. **DATA ANALYSIS AND STATISTICAL PROCEDURES**

### 9.1 **SAMPLE SIZE DETERMINATION**

This is a pilot study to investigate efficacy of vismodegib in different histologic subtypes of BCCs. A total of 36 subjects will be enrolled into the study. The sample size for this study was selected to allow a sufficient number of subjects of histologic subtypes other than nodular BCC, the most common subtype presenting in clinical practices. Superficial BCC and infiltrative/morpheaform subtypes have similar presentation rates. The enrollment method provides assurances that that evaluable data will be available for at least 36 subjects across three subtype groups: infiltrative/morpheaform, superficial, and nodular. Refer to Section 9.2 for details on subgroup type assignment. A sample size of 16 in the nodular group yields a 95% confidence interval of 54%-96% for an observed partial response rate. The nodular group is

included as part of the pilot study, in part, to assess the overall viability of the study. It is important to note that response rate of approximately 75% is anticipated in the nodular group, based on the published literature; the sample size of 16 the nodular group is sufficient to detect this level of efficacy. A sample size of 10 for the infiltrative/morpheaform and superficial BCC groups yields a 95% confidence interval of 10%-70%. Although the confidence intervals are wide, the sample sizes are sufficient to detect a response rate greater the null rate (0%), the expected efficacy level if the treatment had no effect in these histologic subtypes.

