## 9.2 SUBJECT SUB-GROUP ASSIGNMENT

A total of 36 subjects with infiltrative/morpheaform, nodular, or superficial BCC will be enrolled in the study. For patients with multiple BCC lesions, one “target lesion” will be identified and used for subject sub-group assignment for the purposes of enrollment and followed for primary endpoint analysis. For scientific purposes, data from BCC tumors other than “target lesion” will also be collected. The lesion(s) biopsied at Screening Visit will be reviewed and each subject will be assigned to a subtype group as detailed below and in Figure 5.

**Step 1.** Infiltrative/morpheaform subtype lesion will be given priority in subject sub-group assignment.

**Step 2.** If a potential subject does not have a possible target lesion that is infiltrative/morpheaform subtype and has a superficial BCC, then the subject will be assigned to the superficial BCC subtype group.

**Step 3.** If no infiltrative/morpheaform BCC or superficial BCC are identified, then nodular BCC will be eligible for enrollment.

[figure not shown]

Figure 5. Target Lesion Assignment Algorithm

If there are two lesions that may be eligible for target lesion assignment based on histologic subtype, then the lesion with larger clinical dimensions will be designated the “target lesion”. See Appendix 10, Target Lesion Assignment Examples for more information.

This “Target Lesion Assignment Algorithm” will continue in this fashion until any two of the subtype groups reaches 26. This is to ensure that each subgroup has at least 10 subjects. At this point, subjects enrolled must have at least 1 BCC of the remaining subtype group.

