#### **12.10 DEPARTURE FROM PROTOCOL FOR INDIVIDUAL SUBJECTS**

Deviations from a written protocol for individual subjects are inherent to clinical research and can be categorized as either departure from protocol or minor deviations. A “Departure From Protocol” is a deviation of such magnitude as to affect the evaluability of the subject or to potentially compromise the statistical analysis. A departure is usually an emergency or other circumstance that requires a decision be made as to whether the subject should be withdrawn from the study. When a protocol departure or suspected departure occurs; it will be only for that subject. The investigator will contact the study monitor or medical monitor by telephone to report the departure. In the event they are not available, the following emergency number is in operation at all times:

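### Section 9.1's two 95% intervals match Wald intervals that cover only about 90% near the planning rates, and its assurance of at least 36 evaluable subjects allows for no loss (minor)

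*Combined protocol and SAP*

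**What the plan says.** Section 9.1 (Sample Size Determination) describes a pilot in which "A total of 36 subjects will be enrolled into the study". It gives two precision statements. For nodular tumours: "A sample size of 16 in the nodular group yields a 95% confidence interval of 54%-96% for an observed partial response rate", alongside an anticipated response rate of about 75%. For the other two groups: "A sample size of 10 for the infiltrative/morpheaform and superficial BCC groups yields a 95% confidence interval of 10%-70"%, with no response rate given. It concedes that the intervals are wide, and then says that "the sample sizes are sufficient to detect a response rate greater the null rate (0"%).

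The same section states that the enrolment method assures that "evaluable data will be available for at least 36 subjects across three subtype groups". Section 9.2 describes that method, a target-lesion algorithm whose stated purpose is balance: "This is to ensure that each subgroup has at least 10 subjects". Section 8.1 mentions extra subjects only in this form: "The remaining supplies will be made available should additional subjects or study centers be required to reach the enrollment goal of 36 total subjects".

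**The concern.** A 95% interval should contain the true rate in about 95% of repeated studies. At n = 10 and n = 16 the Wald interval is known to fall short, so if these are Wald intervals the stated level is too high. A reader also cannot tell which response rate lies behind the second interval. Sections 9.3.3.1.1 and 9.3.3.1.2 name no interval method for response rates, so the planning method could carry over into the report, where it would matter more.

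The second issue is a count. At least 36 evaluable out of exactly 36 enrolled is possible only if nobody is lost, and the protocol foresees some loss. Section 6.6.2 allows withdrawal and requires it for subjects found ineligible. Section 12.10 defines a departure from protocol as one that "is a deviation of such magnitude as to affect the evaluability of the subject or to potentially compromise the statistical analysis". Evaluable is not defined.

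**Working it through.** **Inputs.** Section 9.1: n = 16, 54%-96%, about 75% (12/16); n = 10, 10%-70%, no rate. The level is two-sided 95%, z = 1.96.

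**Reproducing the printed intervals.** Wald: p ± 1.96 × √(p(1 − p)/n).
- 12/16: 0.75 ± 1.96 × √(0.75 × 0.25/16) = 53.8% to 96.2%, which rounds to 54%-96%.
- 4/10: 0.40 ± 1.96 × √(0.40 × 0.60/10) = 9.6% to 70.4%, which rounds to 10%-70%.

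The other methods tried, at every response count, were Wald with continuity correction, Wald with n − 1, t, Wilson with and without correction, Agresti-Coull, Clopper-Pearson, Jeffreys, logit and arcsine. At n = 10 only Wald at 4/10 matches. At n = 16 Clopper-Pearson at 13/16 (54.35%-95.95%) also rounds to the printed limits, but 13/16 is 81%, not the stated 75%. Wald is the only method tried that fits both groups.

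**Exact coverage at the planning rates.** Sum the binomial probabilities of the counts whose Wald interval contains the true rate.
- n = 16, true rate 75%. Counts 9 to 14 qualify: at 8 the upper limit is 74.5%, and at 15 the lower limit is 81.9%. Sum: 0.0524 + 0.1101 + 0.1802 + 0.2252 + 0.2079 + 0.1336 = 0.9094.
- n = 10, true rate 40%. Counts 2 to 6 qualify: at 1 the upper limit is 28.6%, and at 7 the lower limit is 41.6%. Sum: 0.1209 + 0.2150 + 0.2508 + 0.2007 + 0.1115 = 0.8989.

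**Coverage over surrounding rates** (same enumeration on a fine grid; the ranges are this review's choice):

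| Method | n = 16, rates 60%-90%: mean (min) | n = 10, rates 20%-60%: mean (min) |
|---|---|---|
| Wald | 89.9% (79.9%) | 89.9% (79.0%) |
| Wilson | 95.5% (92.8%) | 95.3% (91.9%) |
| Clopper-Pearson | 97.8% (96.1%) | 97.9% (96.1%) |

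The highest Wald coverage is 94.8% (n = 16) and 94.96% (n = 10), so it never reaches 95% in either range.

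**Replacement limits and widths:**

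| Method | 12/16 | Width (points) | 4/10 | Width (points) |
|---|---|---|---|---|
| Wald | 53.8%-96.2% | 42.4 | 9.6%-70.4% | 60.7 |
| Wilson | 50.5%-89.8% | 39.3 | 16.8%-68.7% | 51.9 |
| Clopper-Pearson | 47.6%-92.7% | 45.1 | 12.2%-73.8% | 61.6 |

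Wilson is narrower than Wald and still covers better, so the shortfall comes mainly from where the Wald interval is centred.

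**Evaluable count.** The documents give no loss rate. If each subject is lost independently with probability d, the chance that all 36 are evaluable is (1 − d)^36. That is 0.99^36 = 70% at 1%, 0.95^36 = 16% at 5% and 0.90^36 = 2% at 10%. These values of d are illustrations, not forecasts. Section 9.2 governs the subtype mix, and Section 8.1 adds subjects only up to 36 enrolled. Neither replaces a non-evaluable subject.

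**The 0% null.** If the true rate is 0%, no response can occur, so a single responder refutes it. The chance of at least one responder in 10 is 1 − (1 − p)^10: 40%, 65%, 89% and 99% at true rates of 5%, 10%, 20% and 40%.

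**The case against.** The strongest reply is that nothing has been miscalculated. The method is inferred, a Wald interval is conventionally labelled 95%, and this is a pilot whose size was chosen mainly to secure enough non-nodular subjects. The section admits that the intervals are wide. Clopper-Pearson also misses 95%, on the high side. Most of this stands, and it is why the point is minor. It does not rescue the label: coverage near 90% is below the stated level, whereas Clopper-Pearson never falls below it and Wilson averages close to it.

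On the evaluable count, Section 6.1.5 has early leavers complete the Week 24 procedures, Section 6.6.2 requires end-of-treatment procedures of treated subjects, and Section 3 schedules assessments every four weeks. Most early leavers would therefore still yield response data. That limits the likely loss but does not turn it into an assurance of none.

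Four stronger readings are tempting but unsupported:
- A reader might infer that the printed nodular interval wrongly rules out a 50% response rate, since Clopper-Pearson reaches 48%. The plan sets no 50% benchmark, and Wilson also just excludes it.
- A reader might infer that the 0% sentence claims useful efficacy. It says only that a rate above zero could be detected, which is true and is already a statement about any activity.
- A reader might object that Wald intervals at 1/10 and 2/10 extend below 0%. Section 9.1 does not make the interval its test of the null.
- A reader might predict a shortfall of evaluable subjects. The procedures above do not support that prediction.

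**Conclusion.** The point holds as a minor correction. The two printed intervals are correctly computed for what they appear to be, but their coverage near the planning rates is about 90% rather than 95%, and the 40% behind the second is unstated. The assurance of at least 36 evaluable from 36 enrolled goes beyond what the enrolment method provides. The 0% sentence is true and could at most be worded more narrowly.

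This rests on the inference that the method is Wald, on 40% as the back-solved rate, and on the nodular group reaching 16 with 10 in each other group (16 + 10 + 10 = 36; Section 3 guarantees only 10 to 16 per group). It does not show that 36 is too few, and no decision rule in the plan uses these limits.

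**What to change.** Keep n = 36.

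1. In Section 9.1, restate the intervals by one named method: Wilson, 51%-90% for 12/16 and 17%-69% for 4/10 (average coverage about 95%), or Clopper-Pearson, 48%-93% and 12%-74% (at least 95% guaranteed, about 98% on average). Either is acceptable. State that 40% is an assumed rate.
2. In Section 9.3.3, say that reported response rates will carry intervals by the same method.
3. In Section 9.1, replace the assurance about evaluable data with the statement that 36 subjects will be enrolled.
4. Optionally, add that a rate above 0% indicates some activity only.

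The cost is a few reworded sentences, with no added subjects or visits. The nodular lower limit falls from 54% to 51% (Wilson) or 48% (Clopper-Pearson). Clopper-Pearson intervals are 1 to 3 points wider than those printed (61.6 − 60.7 = 0.9; 45.1 − 42.4 = 2.7), and Wilson intervals are narrower.
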